4.1.2 Primary Efficacy Variable

Primary efficacy variable will be Clinical pregnancy with fetal heartbeat after the first embryo transfer per randomised patient. If no fresh nor frozen embryo can be transferred, then for the ITT population a negative clinical pregnancy is given for these patients.

4.1.3 Secondary efficacy Variables

Secondary efficacy variables will be the following outcome variables:

- Live birth (Y/N). Will be analysed in a second database lock.
With pass criteria non-inferiority analysis, non-inferiority margin -5%.

STATISTISKA KONSULTGRUPPEN		Statistical Analysis Plan	
Protocol:		Protocol No: <protocol number>	
eValuating iDA Selection Ability. The VISA study.		Version: 2.0	Page 14 of 25

- Positive hCG rate per randomized patient
With pass criteria non-inferiority analysis, non-inferiority margin -5%.
- Non-viable intrauterine pregnancies

Safety Variables

4.1.4 Adverse Events (AE)

The occurrence of adverse events is documented in the eCRF through a separate AE module.

5 STATISTICAL METHODOLOGY

General Statistical Methodology

Primary and all secondary analyses will be performed on ITT population. Complementary analyses will be performed on full analysis set (FAS) and on the per-protocol (PP) population. The primary statistical analyses will be calculation of the mean percentage difference with two-sided 95% confidence interval (CI) regarding the primary efficacy variable Clinical Pregnancy with fetal heartbeat after the first embryo transfer between the iDA group and the trained embryologist (standard) group unadjusted with Farrington-Manning 95% CI. If the lower limit of this 95% CI is larger than -5%, the non-inferiority margin, then non-inferiority is achieved. If non-inferiority is achieved, then we will test primary efficacy variable for superiority with two-sided Fisher's exact test.

Unadjusted and adjusted relative risk (RR) between the two groups with 95% CI will be calculated with Poisson regression model with a robust error variance, (see reference 2) for primary and secondary efficacy variables.

Regarding multiplicity for the primary analysis (clinical pregnancy) and the first two secondary analyses (live birth) and Positive hCG a fixed – sequence test will be applied. (see reference 3)

If non-inferiority is achieved in primary analysis then the probability mass from the primary analysis will be transferred to the first secondary analysis, live birth.

STATISTISKA KONSULTGRUPPEN		Statistical Analysis Plan	
Protocol:		Protocol No: <protocol number>	
eValuating iDA Selection Ability. The VISA study.		Version: 2.0	Page 15 of 25

If non-inferiority is achieved also for live birth then the non-inferiority result for live birth will also be confirmative, and the probability mass will be transferred to the second secondary analysis of positive hCG rate. If non-inferiority is achieved also for positive hCG rate birth, then the non-inferiority results for positive hCG rate will also be confirmative

For the other secondary variables, the p-values will be given for descriptive purpose and no multiplicity adjustment will be performed. These analyses will be considered exploratory.

For unadjusted comparison between the two randomized groups the following tests will be performed: Fisher's exact test for dichotomous variables,

Fisher's non-parametric permutation test for the mean difference between two independent samples for continuous variables,

Mantel-Haenszel chi-square test for ordered categorical variables and

Pearson chi-square test for non-ordered categorical variables.

Dichotomous data will be expressed as numbers and percentages. Continuous variables will be described with mean, standard deviation, median, quartile 25%, quartile 75%, minimum and maximum.

If baseline confounders, variables that differ statistically and clinically between the randomized groups and known to predict primary outcome variable, are found then complementary analyses will be performed adjusted for these baseline variables.

STATISTISKA KONSULTGRUPPEN		Statistical Analysis Plan	
Protocol:		Protocol No: <protocol number>	
eValuating iDA Selection Ability. The VISA study.		Version: 2.0	Page 16 of 25

All tests will be two-tailed and conducted at 0.05 significance level.

All safety analyses will be descriptive by performed embryo selection method.

All analyses will be performed by using SAS® v9.4 (Cary, NC).

Patient Disposition and Data Sets Analysed

The number of subjects included in each of the ITT, FAS, PP and safety populations will be summarized for each treatment group and overall. The number and percentage of subjects randomized and treated will be presented. Subjects who completed the study and subjects who withdrew from study prematurely will also be presented with a breakdown of the reasons for withdrawal by treatment group for the ITT, FAS, PP and safety populations.

Protocol Violations/Deviations

Major protocol deviations are those that are considered to influence the analysis. A list of protocol deviations that were anticipated before the start of the trial was generated. Once the data collection has been finalized and before database lock the steering committee will review all the possible deviations and if needed create additional categories.

The number of patients with major protocol deviations will be summarized per treatment group.

Demographics and Baseline Characteristics

Demographics and baseline characteristics will be summarized by treatment group for the ITT, FAS and PP populations and analysed according to the methods described in section “General Statistical Methodology” above.

STATISTISKA KONSULTGRUPPEN		Statistical Analysis Plan	
Protocol:		Protocol No: <protocol number>	
eValuating iDA Selection Ability. The VISA study.		Version: 2.0	Page 17 of 25

Main Treatment variables

Main treatment variables will be summarized by treatment group for the FAS and PP populations and analysed according to the methods described in section “General Statistical Methodology” above.

Efficacy Analyses

Primary Efficacy Analysis

The primary statistical analyses will be calculation of the mean percentage difference with two-sided 95% confidence interval (CI) regarding the primary efficacy variable Clinical Pregnancy with fetal heartbeat after the first embryo transfer between the iDA group and the trained embryologist (standard) group unadjusted with Farrington-Manning 95% CI. If the lower limit of this 95% CI is larger than -5%, the non-inferiority margin, then non-inferiority is achieved. This analysis will be applied on the ITT population (primary) and PP population (sensitivity analysis). Any inconsistencies in these analyses will be discussed in the study report. Unadjusted relative risk (RR) with 95% CI will also be calculated. The Clinical pregnancy rate with exact 95% CI will be calculated for each of the randomised groups.

The following sensitivity analysis will also be performed adjusted for centre and stratification (minimization) variables:

To account for the lack of independence introduced by both the potential clustering within centers and the optimal randomization process (minimization), we will also estimate the difference in the clinical pregnancy probability between the two randomized groups with a 95% CI using a linear mixed effects regression model (with identity link function) with center as a random effect and fixed effects for the following variables used in the randomization:

- Woman’s age:

STATISTISKA KONSULTGRUPPEN		Statistical Analysis Plan	
Protocol:		Protocol No: <protocol number>	
eValuating iDA Selection Ability. The VISA study.		Version: 2.0	Page 18 of 25

< 25; 25 <= Age < 30; 30 <= Age < 35; 35 <= Age < 40; 5. 40 <= Age

- Number of previous stimulated IVF cycles leading to oocyte pick-up

1-5; 6 – 10; 11 – 15; 16 – 20; 21 – 25; 26 ->

- Number of oocytes:

• 2 – 5; 6 – 10; 11 – 15; 16 – 20; 21 - 25; 26 ->

- Fertilization method:

IVF for all; ICSI for all; ICSI for some

- Number of 2PN oocytes

• 2 – 5; 6 – 10; 11 – 15; 16 – 20; 21 - 25; 26 ->

- Center.

Adjustment with centre as random effect, fertilization method as class variable and the other four as continuous variables.

To account for potential non-constant variance of errors in this model, we will estimate the empirical covariance matrix using the heteroskedasticity consistent method (HC3) as proposed by MacKinnon and White (see reference 1).

Adjusted relative risk (RR) with 95% CI will also be calculated adjusted for the minimization variables using Poisson regression model with a robust error variance.

If non-inferiority is achieved, then we will test the primary efficacy variable for superiority with a two-sided Fisher's exact test. The primary analysis will also be performed per center. If baseline confounders are found the adjusted analyses will also be performed adjusted for these variables.

STATISTISKA KONSULTGRUPPEN		Statistical Analysis Plan	
Protocol:		Protocol No: <protocol number>	
eValuating iDA Selection Ability. The VISA study.		Version: 2.0	Page 19 of 25

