#### **14.6 General statistical methodology**

The main statistical analyses will be calculation of the mean percentage difference with 95% confidence interval (CI) regarding pregnancy rate between the iDAScore group and the trained embryologist group. For comparisons between the two randomized groups Fisher's exact test will be used for dichotomous variables, Fisher's non-parametric permutation test for continuous variables, Mantel-Haenszel chi-square test for ordered categorical variables and Pearson chi-square test for non-ordered categorical variables. For dichotomous variables mean differences and relative risk with 95% CI will be calculated. For continuous variables mean differences between the two groups with 95% CI will be calculated based on Fisher's permutation test and Effect size will be calculated.

Dichotomous data will be expressed as numbers and percentages. Continuous variables will be described with mean, standard deviation, median, quartile 25% and quartile 75%. If baseline confounders, variables that differ between the randomized groups and predict outcome variables, are found then complementary analyses will be performed adjusted for these baseline variables. For adjusted analyses, multivariable logistic regression will be used for dichotomous outcome variables and ANCOVA for continuous outcome variables.

All primary and secondary analyses will be performed on both the ITT-population and the PP population.

All significance tests will be two-sided and conducted at the 5% significance level.

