It is estimated from the results in clinics that clinical pregnancy is estimated to be 35.4% for trained embryologists. If non-inferiority margin is defined as - 5%, the lower limit of the two-sided 95% confidence interval (CI) for the difference between iDAScore group and Trained embryologist group shall not be less than -5% with a probability of 90% ($\beta=10\%$), with an estimation of 5% or more clinical pregnancies in iDAScore group, 494 women per randomization group is needed to show non- inferiority with two-sided Farrington-Manning test. For protection against a 5% loss to follow-up, 1040 patients in total, 520 per group, are needed for recruitment.

STATISTISKA KONSULTGRUPPEN		Statistical Analysis Plan	
Protocol:		Protocol No: <protocol number>	
eValuating iDA Selection Ability. The VISA study.		Version: 2.0	Page 10 of 25

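### An extra adjusted analysis takes its covariates from observed differences between the randomised arms; a covariate set fixed in advance should replace it, for secondary outcomes too

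*SAP*

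**What the plan says.** The SAP (section 5, General Statistical Methodology) provides for complementary analyses adjusted for baseline confounders, defined as "variables that differ statistically and clinically between the randomized groups and known to predict primary outcome variable". Its Primary Efficacy Analysis repeats the provision: "If baseline confounders are found the adjusted analyses will also be performed adjusted for these variables". Protocol 14.6 has a looser form, without the clinical condition and without requiring that the predictor be known beforehand: "If baseline confounders, variables that differ between the randomized groups and predict outcome variables, are found then complementary analyses will be performed". Protocol 14.7 carries the trigger into the primary efficacy analysis.

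Baseline characteristics are compared between arms with the tests of the general section, and the SAP sets all tests at a two-sided 0.05 level. I therefore read a statistical difference as p < 0.05.

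Three other provisions matter here:

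- The non-inferiority decision uses the unadjusted difference with a Farrington-Manning interval.
- For the primary endpoint, the SAP names an adjusted sensitivity analysis that runs whatever the imbalance. It is a linear mixed model with centre as a random effect and maternal age, previous cycles, oocytes, fertilisation method and 2PN count as fixed effects. A relative risk adjusted for the minimisation variables is added.
- The general section also promises adjusted relative risks for the secondary efficacy variables. SAP 5.1.1 sends the secondary analyses back to that section, which names no covariates other than through the trigger.

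**The concern.** In the ITT population, allocation alone produces baseline differences, so a significance test of them cannot show which variables confound the comparison. What makes a covariate worth including is its relation to outcome, and that can be judged before any data are seen. Choosing by observed imbalance leaves out prognostic variables that happen to be balanced. It also means the covariates become known only once the arms have been compared.

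The two further conditions in the SAP do not remove the discretion. No size of difference is given as clinical, and no list or source says which variables count as known predictors.

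At stake is an additional estimate of the primary endpoint that may or may not appear in the report, with contents chosen late. For secondary outcomes there is also no fixed covariate set behind the promised adjusted relative risks. Two of those outcomes, live birth and positive hCG, are in the confirmatory fixed sequence.

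**Working it through.** **1. The plan's own sample size.** Inputs from the SAP, Sample Size calculation: "clinical pregnancy is estimated to be 35.4% for trained embryologists"; "with an estimation of 5% or more clinical pregnancies in iDAScore group", read as +5 points, so 40.4%; "non-inferiority margin is defined as - 5" points; "the lower limit of the two-sided 95% confidence interval (CI"), so z = 1.960; and "shall not be less than -5% with a probability of 90"%, so z = 1.2816.

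n per group = (1.960 + 1.2816)² × (0.354 × 0.646 + 0.404 × 0.596) / (0.05 + 0.05)² = 10.507 × 0.4695 / 0.01 = 493.3, rounded up to 494.

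With the Farrington-Manning null variance the result is 493.7, again 494. Allowing for 5% loss, 494 / 0.95 = 520 per group and 1040 in total. The stated figures reproduce. They rest on the unadjusted analysis, so the covariate rule does not touch them.

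**2. What each provision fixes in advance.**

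| Analysis | Covariates fixed in advance? |
|---|---|
| Primary non-inferiority decision | None needed (unadjusted) |
| Primary endpoint, mixed model and adjusted RR | Yes (centre and minimisation variables; minimisation variables) |
| Primary endpoint, complementary adjusted analysis | No (imbalance trigger) |
| Secondary outcomes, adjusted RR | No (trigger is the only rule given in the general section) |

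The SAP trigger also refers to predictors of the primary outcome, so even as a rule for secondary outcomes it is not tailored to them.

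**3. How often the rule might fire, and with what effect.** The documents give no prognostic strengths, so these are assumptions: three independent, truly prognostic covariates that together explain 2%, 5% or 10% of outcome variance; 520 per arm; simple 1:1 allocation; a linear probability model with HC3 errors; 6000 simulated trials per setting. The rule adjusts for any of the three with p < 0.05 between arms and otherwise keeps the unadjusted result. Minimisation and the clinical condition were not modelled.

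- Firing: 14% to 15% of trials, as expected from 1 − 0.95³ = 14.3%.
- Mean absolute shift when it fires: 0.6 points (R² 2%), 0.9 (5%), 1.3 (10%). The unadjusted standard error at 520 per arm is √(0.4695 / 520) = 3.0 points.
- Change of non-inferiority verdict against the unadjusted analysis: 1.8% to 7.8% of trials in which it fires. Over all trials this is 0.018 × 0.146 = 0.3% to 0.078 × 0.145 = 1.1%.
- Type I error at a true difference of −5 points: rule 2.5% to 3.0%, unadjusted 2.6% to 3.0%, covariates named in advance 2.5% to 2.8% (Monte Carlo standard error about 0.2 points).
- Power at +5 points: rule 91.2% to 91.8%, covariates named in advance 91.4% to 93.8%.

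**4. Analytic check of the precision gain.** With residual variance multiplied by (1 − R²), power at 520 per group is Φ(0.10 / [0.0300 × √(1 − R²)] − 1.96). This gives 91.4% with no adjustment, and 92.0%, 92.7% and 93.9% for R² of 2%, 5% and 10%.

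**The case against.** The SAP requires three conditions together, so significance alone never brings a variable in. The analyses are labelled complementary and carry no pass criterion. The primary endpoint already has adjusted analyses on named covariates. Minimisation makes a material imbalance in those variables unlikely. Adjusting for a prognostic variable that is out of balance is also sensible in itself. Finally, baseline is compared in the per-protocol population as well, where patients are excluded after randomisation and analysed by the selection method actually used. Differences there need not be chance.

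Most of this stands, and it limits the point to the additional adjusted estimates and to the secondary outcomes. It does not rescue the rule. Two of the three conditions are undefined. A set named in advance corrects for a chance imbalance whenever one occurs, without waiting for a test. In the per-protocol population confounding is a real possibility, but a significance test is still a weak way to choose covariates.

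A reader might go further and take 1 − 0.95⁷ = 30% for the seven non-minimised baseline variables in SAP 4.1.1, or 1 − 0.95¹³ = 49% with six pre-randomisation treatment variables added, as the chance that the extra analysis appears. The documents do not support that. Those figures are the chance of any significant baseline test under independence. They ignore the clinical and prognostic conditions, and the list includes height, weight and BMI, which are related.

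**Conclusion.** The point holds in a limited form. The complementary adjusted analysis of the primary endpoint is data-driven, and the adjusted relative risks for secondary outcomes have no fixed covariate set in the general section.

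Two wider inferences should be resisted. The first is that the plan lacks any adjusted analysis named in advance; it has one for the primary endpoint. The second is that the non-inferiority claim is at risk; it rests on the unadjusted interval, and the simulation shows no inflation of type I error.

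The cost of the rule is discretion over a supporting estimate and a small loss of precision: at most about 2.5 points of power at 520 per group (93.9% against 91.4%, R² 10%), comparing a named set with no adjustment. The R² range, the number of prognostic covariates and simple allocation are assumptions. The argument about chance differences applies to ITT only.

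**What to change.** - Delete the imbalance trigger in SAP section 5 (General Statistical Methodology and Primary Efficacy Analysis) and in protocol 14.6 and 14.7.
- State that the covariate set named in the SAP's Primary Efficacy Analysis (centre and the minimisation variables) is the adjusted analysis for primary and secondary outcomes, whatever imbalance is observed.
- Add a further covariate only if it is measured before randomisation and named now. The number of early blastocysts on day 5 is a candidate: it is counted before randomisation (protocol 10.4), already collected, and already an interaction variable in SAP 5.1.4. The documents do not establish its prognostic strength. The restriction to pre-randomisation variables matters because both documents list, under a baseline heading, items settled only after randomisation, such as the morphological score of the transferred embryo.
- Describe baseline data by arm, without using significance tests to choose covariates.
- As a consequential edit, make the title of SAP table 14.2.1.3 refer to all the named allocation variables, not a selection of them.

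The cost is SAP and protocol wording. No new data are needed, the sample size is unchanged, and there is a modest gain in precision for the adjusted estimates.

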## 11.2 Anticipated adverse device effects in the clinical investigation

The identified risks for the investigational device are described in the investigator’s brochure. The table below lists risks anticipated adverse device effects in the current clinical investigation.

| Problem                          | Affects         | Caused by        | Subject withdrawn | Solution   |
|----------------------------------|-----------------|------------------|-------------------|--|
| No iDAScore calculated           | Treatment group | Technical issues | Yes               | Conventional morphology is used to select an embryo for transfer.  |
| Highest scoring embryo overruled | Treatment group | iDAScore ranking | Yes               | Conventional morphology is used to select an embryo for transfer.  |
| No pictures of embryos           | Both groups     | Technical issues | Yes               | Culture dish is removed from the incubator and conventional morphology is assessed using an external microscope. |

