## 16 SAFETY EVALUATION AND REPORTING

Deviations from SOPs or the CIP as well as adverse device effects, device deficiencies and adverse events occurring in the context of the investigation are documented. The definitions and reporting requirements adopted in this investigation are derived from the international standard on clinical investigations ISO 14155:2020, the Medical Device Regulation 2017/745 (MDR), MEDDEV 2.7/3. and MDCG 2020-10/1.

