### 16.2 Recording and reporting of adverse events

The following events are registered (MDR 80:1):

- any adverse event of a type identified in the clinical investigation plan as being critical to the evaluation of the results of that clinical investigation
- any serious adverse event

- any device deficiency that might have led to a serious adverse event if appropriate action had not been taken, intervention had not occurred, or circumstances had been less fortunate
- any new findings in relation to the above events

The events will be registered by the clinic within the adverse events module in the eCRF in a timely manner.

All AEs will be characterized by the following criteria:

- Date of incident
- Intensity or Severity
- Relationship to the investigational device and the related procedure
- Outcome
- Treatment or Action Taken

The investigator shall report events **immediately, but not later than 3 calendar days** after investigational site study personnel's awareness of the event. Any serious adverse events during treatment will be reported as required by national regulations to the relevant authorities. The sponsor is responsible for reviewing all adverse events and ensuring they, if necessary, are reported to the EC and regulatory authorities. The patients involved should be informed as soon as possible. Furthermore, they should be offered counselling and/or support.

If unforeseen technical issues occur, regardless of group affiliation, embryos for transfer will be selected based on morphological assessment only.

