#### Examples of device deficiencies

- No score due to low-quality images or air bubbles
- Cannot access the software for unknown reasons

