5.1.5 Adverse Events

Only treatment-emergent AEs will be included in the summaries for safety population.

A summary of subjects reporting at least one of the following AEs will be presented in an overview table:

- Any AE
- Any SAE
- Any treatment-related AE
- Any treatment-related SAE
- Any AE leading to discontinuation
- *Any device related events*
- Death

Summaries per SOC and PT presenting n (%) of AEs and n (%) of subjects with at least one AE will be provided for:

- All AEs (includes all serious and non-serious AEs)
- All AEs by maximum reported intensity
- All AEs by causality
- All SAEs
- All AEs leading to discontinuation

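### Grouping safety tables by performed selection method would count a registered iDAScore failure in the morphology column; device events should be shown by randomised arm (minor)

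*SAP*

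**What the plan says.** - **Grouping of safety results.** SAP section 5, General Statistical Methodology: "All safety analyses will be descriptive by performed embryo selection method". The AE overview in SAP 5.1.5 includes the row "Any device related events".
- **What happens after a failure.** Protocol 11.2 lists, for the treatment group, a missing score and an overruled top-scoring embryo. For both, the subject is marked as withdrawn and the solution is the same: "Conventional morphology is used to select an embryo for transfer". Protocol 16.2 adds: "If unforeseen technical issues occur, regardless of group affiliation, embryos for transfer will be selected based on morphological assessment only".
- **Who is in the safety population.** SAP 2.1.4 admits subjects who started one of the selection methods.
- **Which deficiencies are recorded.** The opening of Protocol 16 says that "adverse device effects, device deficiencies and adverse events occurring in the context of the investigation are documented". Protocol 16.2 and the summary table in 16.6 are narrower: they register "any device deficiency that might have led to a serious adverse event if appropriate action had not been taken", and extend the test to an absent intervention or less fortunate circumstances. Protocol 16.5 names two examples of deficiencies: "No score due to low-quality images or air bubbles" and "Cannot access the software for unknown reasons".
- **Planned tables.** The AE tables in SAP section 8 (14.3.2.1 to 14.3.2.6) contain none for device deficiencies.

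**The concern.** The investigational device is software, and failing to deliver a usable score is its most direct way of failing. The protocol anticipates this. A table comparing device-related events should therefore keep such a case with the arm that was assigned the device. Grouping by performed method does the opposite on a literal reading: a woman leaves the iDAScore column because the device failed, so the column depends on the event being counted. Where morphology replaced the score, the iDAScore column would hold no failures, and the comparator column would hold those that were registered.

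What is at stake is the descriptive device-safety comparison, not the efficacy conclusion. A reader of the AE overview could not take the device's failure count from the iDAScore column, and no other planned table is designed to give it.

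**Working it through.** The plan gives no figure for failures, so most of the check is a cross-reading.

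**Step 1. Where a failed cycle lands.** Consider a woman randomised to iDAScore for whom no score is produced.

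| Situation | Column in the AE tables |
|---|---|
| Failure not registered | Neither |
| Registered, grouped by method performed (SAP section 5) | Morphology |
| Registered, grouped by method started (the term in SAP 2.1.4), if opening an iDAScore assessment counts as a start | iDAScore |

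The three outcomes exclude one another. SAP section 5 is the only sentence that sets the grouping, and it points to the second row. An overrule is less clear: the software ran and ranked the embryos, but Protocol 11.2 says morphology made the selection. The SAP does not say which method was then performed.

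**Step 2. Whether the failure is registered.** The opening of Protocol 16 has no severity filter; 16.2 and 16.6 have one. Their test is counterfactual: it asks what might have happened without the corrective action. Falling back to morphology is such an action, so a harmless course after the fallback does not settle the test. The two deficiencies named in 16.5 are neither clearly in nor clearly out, and sites could decide differently.

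**Step 3. Size.** The only plan figure used is 520 per arm, from the sample size section of both documents. It reproduces: 494 / (1 - 0.05) = 520. The failure or overrule rate r is an assumption, with a range of 0.5% to 5%. Further assumptions are that every case is registered, that all 520 women per arm are in the safety population, and that there is no other crossover. Then k = 520 × r, rounded, and the performed-method denominators are 520 - k and 520 + k.

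| r | k | By randomised arm (iDAScore vs control) | By performed method (iDAScore vs morphology) |
|---|---|---|---|
| 0.5% | 2.6, so 3 | 3/520 vs 0/520 | 0/517 vs 3/523 |
| 1% | 5.2, so 5 | 5/520 vs 0/520 | 0/515 vs 5/525 |
| 2% | 10.4, so 10 | 10/520 vs 0/520 | 0/510 vs 10/530 |
| 5% | 26 | 26/520 vs 0/520 | 0/494 vs 26/546 |

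At every assumed rate the direction of the comparison reverses. (The 494 in the last row is 520 - 26; that it equals the evaluable sample size is a coincidence.)

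**The case against.** The strongest case on the other side has five parts.

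- **Failures are visible elsewhere.** Protocol 11.2 marks these subjects as withdrawn. SAP section 5 breaks withdrawal reasons down by treatment group, including for the safety population, and counts major deviations per treatment group. This stands: a trace survives outside the AE tables. It is not a device-failure count, and it depends on how reasons and deviations are coded.
- **The main safety signal is not moved.** Protocol 14.4 treats pregnancy outcomes as safety variables, and the SAP analyses them on ITT by randomised group. This stands, and it rules out any inference that the primary result is at risk.
- **The registration rule does not clearly exclude the named deficiencies.** This also stands. A reader might infer that failures are filtered out and never appear against the device. The documents do not support that: the test is counterfactual, Protocol 16 says deficiencies are documented, and 11.2 lists a missing score among anticipated adverse device effects. Nor can one failure be both unregistered and counted in the wrong column.
- **An overrule is not a malfunction.** Protocol 7.1 leaves the final decision to a medical professional. This stands, and overrules should be counted separately.
- **Grouping safety by method received is a common convention, and no test depends on it.** This stands for adverse events in general, such as the complications of stimulation or oocyte pick-up named in 16.5. It does not answer the point for device failures, where the event itself changes the method received. Causality is assessed against the device in either group (Protocol 16.4), so a careful reader might recognise a crossover, but the table would not show it.

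**Conclusion.** The concern holds in a limited form. On a literal reading of SAP section 5 with Protocol 11.2 and 16.2, a registered iDAScore failure is counted under conventional morphology in the row for device-related events. The unreconciled terms started and performed leave another reading open, which is itself a reason to clarify.

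No rate is stated in the documents. The 3 to 26 women in the working rest on the assumed 0.5% to 5% and on every case being registered, and they pool failures with overrules. The direction of the misassignment does not depend on the rate.

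Two stronger conclusions are not supported: that failures would be absent from the results altogether, and that the non-inferiority analysis is affected. The severity is minor.

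**What to change.** **SAP section 5, 5.1.5 and section 8.** Tabulate device-related events and device deficiencies by randomised arm. Inside the iDAScore arm, split cycles into scored and followed, no score or no access, and overruled, with overrules counted apart from malfunctions. The AE tables by performed method may stay as a supplement.

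**SAP 2.1.4 and section 5.** Reconcile started with performed, and state in which column an overruled or unscored cycle is placed.

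**Protocol 16, 16.2 and 16.6.** Reconcile the general statement that deficiencies are documented with the registration rule based on SAE potential, so that the deficiencies named in 16.5 are recorded in the eCRF. Reporting to authorities is unchanged.

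**Cost.** One table shell, a few sentences in the SAP, an edit to the registration wording, and a short site entry for each failed score. The device's failure count may look less favourable. Embryo selection and the efficacy analyses do not change.
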